3.5 Endpoints

3.5.1 Primary Endpoint

Success rate in IGA at Week 4: percentage of subjects with IGA score of 0 or 1 with improvement by at least 2 grades. Subjects with missing IGA data will be handled as non-responders.

[Rationale for Primary Endpoint]

Investigator's Global Assessment evaluates the systemic clinical characteristics (erythema, infiltration, papulation, oozing, and crusting) by the severity score of IGA (0 = Clear, 1 = Almost clear, 2 = Mild disease, 3 = Moderate disease, 4 = Severe disease/Very severe disease) and clearly distinguishes each score. In patients with AD, as remission or close to remission is the goal of the treatment¹, clinical characteristics of remission or close to remission are defined as IGA score of 0 (Clear) or 1 (Almost clear), and clinically significant improvement as improvement in IGA by at least 2 grades.

Based on the above, the success rate in IGA (percentage of subjects with IGA score of 0 or 1 with improvement by at least 2 grades) at Week 4 is established as the primary efficacy endpoint.

3.5.2 Secondary Endpoints

- Success rate in IGA at Week 4: percentage of subjects with IGA score of 0 or 1
- Change from baseline in IGA at Week 4
- Success rate in EASI 75 (improvement $\geq 75\%$ in EASI), EASI 90 (improvement $\geq 90\%$ in EASI) and EASI 50 (improvement $\geq 50\%$ in EASI) at Week 4
- Change from baseline in the total score of EASI and each clinical sign score at Week 4
- Change from baseline in Verbal Rating Scale (VRS) for pruritus at Week 4
- Change from baseline in VRS for pruritus up to Day 7

- Change from baseline in the total score of Patient-Oriented Eczema Measure (POEM) at Week 4
- Change from baseline in the total affected BSA (%) at Week 4

3.5.3 Safety Endpoints

- Adverse events
- 1) AEs occurring after the start of IMP administration (Treatment-emergent adverse event [TEAE])
- 2) TEAEs by severity
- 3) TEAEs resulting in death
- 4) Serious TEAEs
- 5) TEAEs leading to discontinuation of IMP administration
- 6) TEAEs (skin and subcutaneous tissue disorders) by grade
- 7) TEAEs at treatment areas
 - Clinical laboratory tests
 - Vital signs and body weight

3.6 Measures to Minimize/Avoid Bias

This trial is a randomized, double-blind trial.

The IMP allocation manager will prepare a master “random allocation table” (hereinafter, “randomization table”) and conduct IMP coding according to the operating procedures for randomization. Also, the IMP allocation manager will prepare an emergency code list for use in emergencies such as the occurrence of a SAE.

The investigator, subinvestigator, and subjects are blind to the IMP randomization code. Except for some designated personnel, the sponsor’s trial staff, including the personnel of contract research organizations, are also unable to access the IMP randomization code during the trial period.

The emergency code list will be kept under strict control by the registration system until the end of the trial. If a medical emergency occurs in a subject and knowledge of his or her IMP randomization code is considered important for treatment, the emergency code will be broken according to “[5.7 Procedure for Breaking the Blind](#).”

When IMPs are recovered by the sponsor prior to unblinding, they are to be recovered sealed by the IMP manager.

Protocol 271-102-00008

The subjects will be allocated using dynamic allocation (minimization method). Details will be provided in a separate specification.

3.7 Trial Procedures

[Table 3.7-1](#) shows the schedule of assessment.

Table 3.7-1 Schedule of Assessments

Evaluation	Screening period (2–30 days)		Assessment period (4 weeks)			
	Screening examination	Baseline examination	Week 1 examination ^a (± 2 days) ^b	Week 2 examination ^a (± 3 days) ^c	Week 4 examination ^a (± 3 days) ^c Withdrawal examination ^d	Unscheduled visit
Informed consent	○ ^e					
Inclusion and exclusion criteria	○	○				
Subject demographics	○					
Physical examination	○	○	○	○	○	○ ^f
Vital signs and body weight	○	○	○	○	○	○ ^f
Clinical laboratory tests	○	○			○	○ ^f
Pregnancy test ^g	○	○			○	○ ^f
IGA	○	○	○	○	○	○ ^f
EASI	○	○	○	○	○	○ ^f
VRS for pruritus ^h		○ ⁱ ← → ○ ⁱ		○	○	○ ^f
POEM		○	○	○	○	○ ^f
Affected BSA	○	○	○	○	○	○
Treatment area		○	○	○		○ ^f
Administration diary		○ ^j ←		→ ○		
Severity of AD	○	○				
Photograph of the target site		○	○	○	○	○ ^f
Status of IMP administration			○	○	○	
Prescription and collection of IMP		○ ^k	○ ^l	○	○ ^m	○ ^l
IMP administration		○ ⁿ ← →				
AEs	←				→	
Concomitant medications and therapies	←				→	
Patch test ^o		←			→	

^aThe reference date of the Week 1 examination, Week 2 examination and Week 4 examination will be the same day of the week as the baseline examination.

^bAcceptable window of ± 2 days

^cAcceptable window of ± 3 days

^dWithdrawal examination should be conducted as soon as possible.

^eInformed consent is to be obtained prior to screening examination (possibly on the same day).

^fIs to be conducted, as necessary.

^gShould be conducted only for female children aged 7 to 14 years old.

^hShould be conducted only for female children aged 7 to 14 years old (at time of obtaining informed consent). The most intense pruritus in the past 24 hours will be evaluated. The investigator or subinvestigator will interview the subjects during scheduled visits after the baseline examination.

ⁱThe subjects will keep a pruritus diary once daily, every day, at the same time in principle as the time of baseline examination from the day after the baseline examination until the day before the Week 1 examination. However, the subjects should keep the pruritus diary up to Day 8 if they are to visit on Day 9 or later.

^jThe subjects should keep an administration diary every day from the baseline examination to the Week 4 examination (withdrawal examination).

^kOnly IMP prescription.

^lIMP will be additionally prescribed, as necessary.

^mOnly IMP collection.

ⁿThe IMP administration should be started at the trial site after all baseline examinations are finished.

^oIf any AE of suspected hypersensitivity occurred at the treatment area, verbal consent should be obtained again from the subject to conduct a patch test, and the patch test should be conducted according to the procedure (see [Section 5.5, Implementation of Patch Test](#))

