- Subjects who are unable to stop using topical corticosteroids for skin (excluding scalp) categorized as low or medium potency in the “Guidelines for Management of Atopic Dermatitis” from 4 days prior to the baseline examination until the Week 4 examination.
- Subjects who are unable to continue in the trial without changing the dosage and administration of systemic antihistamines, sodium cromoglicate, tranilast, or suplatast

	tosilate from 7 days prior to the baseline examination until the Week 4 examination
Trial Sites:	Approximately 30 sites in Japan

Investigational Medicinal Product(s), Dose, Dosage regimen, Treatment period, Formulation, Mode of Administration:	Test Product: 0.3% and 1% OPA-15406 Ointment or vehicle Twice daily administration for 4 weeks
Trial Assessments:	Efficacy: IGA, Eczema Area and Severity Index (EASI), Verbal Rating Scale (VRS) for pruritus, Patient-Oriented Eczema Measure (POEM), affected BSA Safety: Adverse events, physical examination, vital signs, body weight, and clinical laboratory values Screening/Other: Medical history, previous medications and pregnancy test
Criteria for Evaluation:	Primary Endpoint: Success rate in IGA at Week 4: Percentage of subjects in whom IGA score is 0 or 1 and improved at least 2 grades from baseline. Secondary Endpoints: Success rate in IGA at Week 4: Percentage of subjects in whom IGA score improves to 0 or 1, success rates in EASI 75 (improvement $\geq 75\%$ in EASI), EASI 90 (improvement $\geq 90\%$ in EASI), and EASI 50 (improvement $\geq 50\%$ in EASI) at Week 4, changes from baseline in each parameter (IGA, EASI, VRS for pruritus [7 - 14 years of age only], POEM, affected BSA) at Week 4, and change in VRS for pruritus from baseline to Day 7. Criteria for Safety Evaluation: Adverse events, clinical laboratory values, vital signs, and body weight.

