3.3 Trial Population

3.3.1 Number of Subjects and Description of Population

The target population of this trial is pediatric AD patient with an IGA score of 2 or 3. Subjects will be included in the trial to reach the target number of 240 subjects for IMP administration (the target inclusion ratio for “2 - 6 years old” and “7 - 14 years old” of age is 1:1). Any withdrawals will not be supplemented.

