3.4.2 Inclusion Criteria

Subjects are required to meet the following inclusion criteria #1 through #7 in [Table 3.4.2-1](#) at the screening examination, and #6 and #7 at the screening examination and the baseline examination.

Table 3.4.2-1 Inclusion Criteria	
1	Sex: Either male or female
2	Hospitalization status: Outpatient
3	Age: 2 to 14 years, inclusive (at time of obtaining informed consent)
4	Able to obtain written informed consent from the subject's legal guardian
5	Diagnosis of AD based on the Japanese Dermatological Association's criteria ¹ (refer to Appendix 1)
6	Atopic dermatitis affecting $\geq 5\%$ to $\leq 40\%$ of BSA (excluding scalp)
7	IGA score of 2 or 3

[Rationale for Inclusion Criteria]

- 1) Atopic dermatitis occurs in both males and females.
- 2) Most patients to be included in this trial are outpatients.
- 3) The phase 2 trial (Trial 271-102-00002) in Japan was conducted in pediatric patients (aged 2 - 14 years old), showing efficacy OPA-15406 ointment without no particular safety concerns. Therefore, subjects aged 2 to 14 years old are included in the present trial.
- 4) To conduct the trial without any ethical problems.
- 5) Patients with AD who meet the Japanese Dermatological Association's criteria are included in order to evaluate the efficacy and safety of the IMP in AD patients in Japan.
- 6)-7) To appropriately evaluate the efficacy of the IMP on the target disease.

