3.7.1.6 Randomization (Allocation of Investigational Medicinal Products to Subjects)

The investigator or subinvestigator will enter the necessary information for the subject's eligibility in the IWRS. On the day of the baseline examination, the subjects confirmed to be registered in the IWRS will be allocated to the 0.3% OPA-15406 group, 1% OPA-15406 group, or vehicle group. The investigator or subinvestigator will confirm the allocation result and the amount of IMP to be prescribed for 2 weeks on the IWRS screen displaying the registration result, and prescribe the IMP. The weight of the dispensed IMP will be measured (unit in g; rounded to the one decimal place; same method for all subsequent IMP weight measurements hereinafter). The IMP administration will be started at the trial site after all baseline examinations are finished. The investigator or subinvestigator will instruct the subjects to record the status of IMP administration in the administration diary daily and bring the diary with them to their next visits.

Information on randomization (date of randomization or registration, subject number or treatment group) will be recorded in the source document and CRF.

3.7.1.7 Between the Day After the Baseline Examination and the Day Prior to the Week 1 Examination

The investigator or subinvestigator will instruct the subject to evaluate and record the following item in the pruritus diary in relation to the most intense pruritus in the past 24 hours once daily, every day, at the same time as the baseline examination in principle from the day after the baseline examination to the day before the Week 1 examination. However, the subject will keep the pruritus diary up to Day 8 if scheduled to visit on Day 9 or later.

- VRS for pruritus (only for subjects aged 7 - 14 years old)

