3.12 Subject (including Subject’s Legal Guardian) Compliance

- To avoid using drugs that are not permitted by the investigator or subinvestigator.
- To thoroughly understand the details of the administration guidance and follow it.
- To keep an administration diary every day.
- The subject will evaluate the most intense pruritus in the past 24 hours once daily, every day, at the same time as the baseline examination in principle from the day after the baseline examination until the day before the Week 1 examination and describe it in a pruritus diary for subjects aged 7 to 14 years old. However, the subject will keep the pruritus diary up to Day 8 if scheduled to visit on Day 9 or later.
- When bathing or taking a shower, to administer the IMP afterwards.
- To visit the trial site on the specified visit days during the trial period.
- To bring the IMP, administration diary, and pruritus diary as instructed.
- To avoid excessive exercises, getting a suntan, and excessive drinking and eating and to keep regular hours to prevent possible effects on safety.
- Information obtained during participation in this trial must not be disclosed to any third party.

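### Footnote h of the Schedule of Assessments limits the pruritus VRS to girls aged 7 to 14, while the rest of the protocol requires it in all subjects of that age; sites that follow the footnote would lose the boys' VRS data

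*Protocol*

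**What the plan says.** Table 3.7-1 (protocol Section 3.7) attaches footnote h to the VRS row. The footnote restricts the assessment to girls aged 7 to 14 by age at consent, then defines what is rated: "The most intense pruritus in the past 24 hours". Footnote g, on the pregnancy test, opens with the same restriction. The daily pruritus diary (footnote i) sits in the same row.

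Elsewhere the limit is age alone:

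- Synopsis, Criteria for Evaluation: "VRS for pruritus [7 - 14 years of age only".
- Section 3.7.1.7 (diary period): "VRS for pruritus (only for subjects aged 7 - 14 years old". Section 3.7.1.5 (baseline) and Sections 3.7.1.8 to 3.7.1.11 (Weeks 1, 2 and 4, withdrawal and unscheduled visits) use the same wording.
- Section 3.12, on subject compliance: "describe it in a pruritus diary for subjects aged 7 to 14 years old".

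Section 3.4.2 admits both sexes: "Sex: Either male or female". Section 3.5.2 lists two VRS endpoints with no sex limit: "Change from baseline in Verbal Rating Scale (VRS) for pruritus at Week 4" and "Change from baseline in VRS for pruritus up to Day 7". The VRS method (protocol Section 3.7.5.3) and the SAP (Sections 3.4, 6.2, 8.2.5 and 8.2.6) set no sex limit either.

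**The concern.** The footnote is an operative instruction in the visit schedule. Read literally, it removes both the VRS interview and the diary for every boy aged 7 to 14. It is also the only place that ties the VRS age limit to age at consent, so a site unsure about a child close to 7 would look there. Neither document says whether table or text prevails, and Section 3.13 requires all deviations to be recorded, so a site that follows one departs from the other.

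The loss would be permanent. The VRS rates the past 24 hours, so a missed baseline or diary day cannot be rebuilt. The SAP analyses change from baseline with baseline as covariate (Section 8.2.2, applied to VRS by 8.2.5 and 8.2.6). A boy with no baseline VRS therefore contributes to neither endpoint. If sites read the protocol differently, the VRS set would be selected by site and sex.

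**Working it through.** **1. Which statement is the odd one out?**

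| Place in protocol | Age limit for VRS | Sex limit for VRS |
|---|---|---|
| Table 3.7-1, footnote h | 7-14 | girls only |
| Synopsis | 7-14 | none |
| 3.7.1.5, 3.7.1.7 to 3.7.1.11 | 7-14 | none |
| 3.12 | 7-14 | none |
| 3.5.2, 3.7.5.3 | not restated | none |

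Only the footnote restricts by sex. No rationale for a girls-only itch score appears in either document. The opening shared with footnote g points to a copying slip.

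**2. Inputs for size.**

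- 240 subjects, 80 per group (protocol Section 7.1).
- Age mix (protocol Section 3.3.1): "the target inclusion ratio for “2 - 6 years old” and “7 - 14 years old” of age is 1:1".
- Share of boys, b: not given, and there is no sex quota. Assumed 50%, range 40-60%.

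The documents state no sample size or power for the VRS. Their one stated figure, 72 per group for IGA success of 36% against 12% at 90% power, comes out at 73 with the continuity-corrected two-proportion formula (65 uncorrected) and does not depend on the VRS.

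**3. Intended VRS set.** 240 × 1/2 = 120 children; 120 / 3 = 40 per arm.

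**4. Worst case: every site follows the footnote.** Per arm = 40 × (1 − b). The standard error of a difference between two arms is multiplied by 1/√(1 − b).

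| Boys | Total | Per arm | SE factor |
|---|---|---|---|
| 40% | 72 | 24 | √(40/24) = 1.29 |
| 50% | 60 | 20 | √(40/20) = 1.41 |
| 60% | 48 | 16 | √(40/16) = 1.58 |

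**5. What that means for power (illustration).** At 40 per arm, two-sided 5% and 80% power, the detectable difference is (1.96 + 0.84) × √(2/40) = 0.63 SD. For that same difference, power falls to about 58%, 51% and 43% at 24, 20 and 16 per arm.

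**6. Mixed reading.** If sites enrolling a fraction f of the children follow the footnote, per arm = 40 × (1 − f × b). With f = 0.5 and b = 0.5 this is 40 × 0.75 = 30, and the SE factor is √(40/30) = 1.15.

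**The case against.** The strongest reply is that this English text is a translation, dated 9 April 2019, of a protocol issued on 1 February 2019 for about 30 sites, all in Japan. The amendment appendix shows that the translation altered at least one term. The original is not available here, so the sex restriction may exist only in the English. That stands: what sites actually held is not established, and the original has to be checked first.

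The second reply is that the visit-by-visit lists repeatedly tell investigators to assess all subjects aged 7 to 14, and that a careful reader would recognise the slip. This also stands, and makes the loss conditional. It does not remove the contradiction, because nothing ranks the text above the table.

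A reader might infer more than the documents support:

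- *Half the VRS data would be lost.* This needs every site to follow the footnote and a near-equal sex mix. Neither is documented.
- *Boys would have no itch data at all, or the diary is the only early itch measure.* POEM is collected in both sexes at baseline and Weeks 1, 2 and 4, and its first question asks about itchy days. The VRS interview is also scheduled at Week 1, although the footnote would restrict that too. What only the diary supplies is daily itch intensity in the first week. POEM is analysed as a total, so its itch item is a partial substitute.
- *The treatment comparison would be biased.* Allocation is randomised and blinded, so a restriction by sex applies regardless of arm. The cost is in precision and generalisability.

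Inferential weight is also limited: the closed testing procedure covers only the two primary comparisons, and EASI 75 is the secondary endpoint singled out as important.

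**Conclusion.** Footnote h is wrong as written: it contradicts every other statement of the VRS population. This is an internal inconsistency, most likely clerical, and not a design choice. The harm is conditional on a site following the table over the visit text, but where that happens the boys' baseline, diary and visit VRS are gone for two secondary endpoints.

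The upper bound is a fall from about 40 to 16-24 per arm, with a standard error 1.3 to 1.6 times as large. It rests on the 1:1 age target being met, equal arms, an assumed 40-60% boys, and all sites following the footnote. Partial adherence costs less. IGA, EASI, POEM and affected BSA are unaffected. The point is worth correcting because the data cannot be recovered and the correction is trivial.

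**What to change.** In footnote h of Table 3.7-1, replace 'female children' with 'subjects', keeping the clause that fixes age at consent. Leave footnote g as it is. Check the original-language protocol for the same error. If it is there, correct it and notify sites that the VRS interview and pruritus diary apply to boys and girls aged 7 to 14. If it is not, only the translation needs correcting.

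The cost is a wording change in one footnote and, if needed, one site notice. It adds no procedure beyond those the visit sections already require.

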3.7.1 Schedule of Assessments

Regarding assessments to be performed by the investigator or subinvestigator, the tasks that a clinical trial associate is able to perform (eg, subject demographics survey and tasks related to clinical laboratory tests) may be performed by the clinical trial associate under the supervision of the investigator.

3.7.1.1 Acquisition of Informed Consent

The investigator or subinvestigator will obtain written consent from the subject's legal guardian. The investigator or subinvestigator will assign a subject identification number ([3 digit number of site ID] + subject number [S + 5 digit serial number starting from 00001]) to the subject providing consent.

3.7.1.2 Screening Examination

After acquisition of informed consent, the investigator or subinvestigator will perform the following examinations, observations, and evaluations, and select subjects who meet the inclusion criteria and do not fall under any of the exclusion criteria.

- Subject demographics
- Physical examination
- Vital signs and body weight
- Clinical laboratory tests
- Pregnancy test (only for female children aged 7 - 14 years old)
- IGA
- EASI
- Affected BSA
- Severity of AD
- AEs
- Concomitant medications and therapies

Investigator or subinvestigator will record the results of the eligibility of subjects on the list of screened subjects and the list of enrolled subjects.

3.7.1.3 Subject Demographics

The investigator or subinvestigator is to record the following information in the source document and CRF.

- Date of informed consent
- Sex
- Date of birth

- Height (unit in cm: measurement indicated as an integer value; if measurement to one decimal place is possible, then the number is to be rounded to nearest integer value.)
- Complications
- Date of onset of AD
- Medical history (within 6 months prior to the date of informed consent)
- In- or outpatient status (outpatient)
- Subject identification number
- Country where the trial is conducted (Japan)
- Race
- Ethnicity
- Possibility of pregnancy

3.7.1.4 Subject Registration

The investigator or subinvestigator will register all subjects in the Interactive Web Response System (IWRS).

3.7.1.5 Baseline Examination (2 - 30 Days After the Screening Examination)

The investigator or subinvestigator will perform the following examinations, observations, and evaluations, and record the results in the source document and CRF.

- Confirmation of inclusion/exclusion criteria
- Physical examination
- Vital signs and body weight
- Pregnancy test (only for female children aged 7 - 14 years old)
- IGA
- EASI
- VRS for pruritus (only for subjects aged 7 - 14 years old)
- POEM
- Affected BSA
- Treatment area
- Severity of AD
- Photograph of the target site
- AEs
- Concomitant medications and therapies

3.7.1.6 Randomization (Allocation of Investigational Medicinal Products to Subjects)

The investigator or subinvestigator will enter the necessary information for the subject's eligibility in the IWRS. On the day of the baseline examination, the subjects confirmed to be registered in the IWRS will be allocated to the 0.3% OPA-15406 group, 1% OPA-15406 group, or vehicle group. The investigator or subinvestigator will confirm the allocation result and the amount of IMP to be prescribed for 2 weeks on the IWRS screen displaying the registration result, and prescribe the IMP. The weight of the dispensed IMP will be measured (unit in g; rounded to the one decimal place; same method for all subsequent IMP weight measurements hereinafter). The IMP administration will be started at the trial site after all baseline examinations are finished. The investigator or subinvestigator will instruct the subjects to record the status of IMP administration in the administration diary daily and bring the diary with them to their next visits.

Information on randomization (date of randomization or registration, subject number or treatment group) will be recorded in the source document and CRF.

3.7.1.7 Between the Day After the Baseline Examination and the Day Prior to the Week 1 Examination

The investigator or subinvestigator will instruct the subject to evaluate and record the following item in the pruritus diary in relation to the most intense pruritus in the past 24 hours once daily, every day, at the same time as the baseline examination in principle from the day after the baseline examination to the day before the Week 1 examination. However, the subject will keep the pruritus diary up to Day 8 if scheduled to visit on Day 9 or later.

- VRS for pruritus (only for subjects aged 7 - 14 years old)

